3.15.2 Clinical Laboratory Evaluation

Continuous laboratory data will be summarized using descriptive statistics of actual values and changes from baseline over time at each scheduled assessment timepoint (i.e., as defined in the Schedule of Events; [Table 11](#) and [Table 12](#)). These data will also be categorized as low, normal, or high based on the reference ranges of the central laboratory.

The set of clinical laboratory tests are provided in [Appendix 2](#). Note, the lab parameter Tyr, will also be summarized as a clinical laboratory test, but in a separate table.

For each of the 3 study periods (i.e., DEP, RWP, and OLE), shift tables for hematology and serum chemistry parameters summarizing the number and percentages of participants who had both DEP baseline and at least one post baseline measurements will be displayed (i.e., using the DEP baseline as the reference for all 3 study parts). Both the lowest and highest value of post-baseline assessments will be used. For this analysis, any lab collection performed on unscheduled analysis visits will be included. The set of hematology and serum chemistry parameters which have corresponding Low/Normal/High assessments will be included.

For the RWP the results will be presented by treatment group; and presented overall for the DEP and OLE.

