plasma TCA and urine HA) were observed. In the biomarker study, the production of TCA in the fasted state was similar in magnitude to the production after a protein load in the SYNB1618-treated subjects. No TCA production was observed in the placebo group. This supports strain activity in the fasted state, regardless of dietary Phe intake.

No treatment-related SAEs were reported. As in the SYNB1618-CP-001 study, mild to moderate GI AEs were observed in a dose-related fashion. Nausea and vomiting were the dose-limiting symptoms. The MTD was determined to be  $2 \times 10^{12}$  live cells TID. A small, dose-related increase in C-reactive protein (CRP) was observed in some participants; the clinical significance of this finding is unclear, and no AEs appeared to be related to CRP increases. The CRP level returned to normal after the end of dosing in those participants who had a follow-up sample available.

SYNB1618-CP-003 (SynPheny-1) was a Phase 2, open-label study of the efficacy and safety of SYNB1618 and SYNB1934 in participants with PKU, designed as a proof-of-concept study to show Phe lowering, relative to baseline. This 2-arm study used a dose-ramp regimen consisting of 4 dose levels of SYNB1618 ( $1 \times 10^{11}$ ,  $3 \times 10^{11}$ ,  $1 \times 10^{12}$ , and  $2 \times 10^{12}$  live cells) over 15 days of treatment in Arm 1, and 4 dose levels of SYNB1934 ( $3 \times 10^{11}$ ,  $6 \times 10^{11}$ ,  $1 \times 10^{12}$ , and  $2 \times 10^{12}$  live cells) over 15 days of treatment in Arm 2. The treatment period was preceded by a 6-day diet run-in period, with concomitant PPI administration throughout the treatment period. A tracer study, using D5-labeled Phe, and a biomarker study were conducted.

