## 1.7. Benefit-Risk Assessment

SYNB1934 and its closely related strain SYNB1618 have been studied in more than 230 HVs and PKU participants. The safety profile has been consistent with the probiotic chassis EcN, which has been used in participants for decades in the European Union and Canada without requirement for prescription. There have been no treatment-related SAEs, no deaths, no systemic toxicity, and no infections. Interindividual variability in tolerability has been observed. The majority of TEAEs have been either mild or moderate in severity and reversible. Most AEs have been GI-related and included GI discomfort, nausea, and vomiting. At increasing doses, GI-related AEs, mainly nausea and vomiting, have been dose limiting. A small dose-related and reversible increase in CRP has been observed in some participants; the clinical significance of this finding is unclear. The CRP level has returned to normal after end of dosing.

Consistent with the design of SYNB1934, clearance is rapid following discontinuation of dosing. In study SYNB1618-CP-001, SYNB1618 was cleared within 4 days following the last dose, as indicated by fecal quantitative polymerase chain reaction (qPCR) analyses. Data from study SYNB1618-CP-002 are consistent. Across all study parts, following up to 7 days of repeat dosing with SYNB1618, no fecal sample was above the limit of quantification at 7 days after last dose. In neither study was there any evidence of colonization, nor did any participant require antibiotic treatment to achieve clearance. Clearance data for SYNB1934 are consistent with that for SYNB1618 with no subject having a positive qPCR sample more than 1 week after the last dose.

Data from completed studies demonstrates that SYNB1934 can access Phe from within the GI tract, as demonstrated by the D5-Phe meal challenge. A dose-related decrease in plasma D5-Phe AUC has been observed, with corresponding increase in strain-specific biomarkers plasma D5-TCA and urinary D5-HA. In the Phase 2 study SYNB1618-CP-003, SYNB1934 led to a mean 34% decrease in plasma Phe in PKU participants, thus demonstrating potential for clinical benefit in the treatment of PKU. Individual variability in Phe lowering was observed. Data from HVs in SYNB1934-CP-001 demonstrate increased Phe conversion capacity of SYNB1934 compared to SYNB1618 based on strain-specific biomarkers.

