**Table 5: Schedule of Events: Dose-escalation (Part 1) and Randomized Withdrawal (Part 2)**

Description/Week a	Screen b	DEP (Part 1)			RWP (Part 2)		
		Study/DEP Baseline	iTD-Finding Period	End of DEP b (RWP Baseline) c	Wk 1	Wk 3	Wk 4 (OLE Baseline) c
Study Day	-45 to -1	1	Up to 105 days d	21 days after iTD	7	21	28
Assessmentb (Protocol Section)							
Informed consent (11.5)	•						
Medical history and prior medications (5.2)	•						
Vital signs (SBP/DBP, pulse, body temperature, height, weight e ) (5.5.2)	•	•		•			•
Physical examination (5.2)	•						
FSH test (postmenopausal women only) (5.5.3)	•						
Pregnancy test (WOCBP only) f (5.5.3)	•	•		•			•
Record concomitant medications (4.3.4)	•	•	•	•	•	•	•
Adverse event reporting (5.5.1)	•	•	•	•	•	•	•
Collection of adverse event diary cards (5.5.1)		•	•	•	•	•	•
Weekly contact by site personnel (telephone, text, email)			•	•	•	•	•
Randomization (8.11)				•			
Blood Phe g and Tyr (5.4.1)	•	•	•	•	•	•	•
3-Day dietary intake assessment h (3.3)		•	•	•	•	•	•
Administer PPI once per day (4.3.4.1)	• i	•	•	•	•	•	•
IMP immediately after meals j (3.2)		•	•	•	•	•	•
Laboratory tests (hematology/CBC with differential, CRP, serum chemistry, urinalysis) (5.5.3)	•	•		•			•
Electrocardiogram (supine for 5 minutes)(5.5.2)	•						
Immunogenicity sample k (5.2)		•					
Optional fecal sample for microbiome analysis l (5.2)	•						

AE = adverse event; CBC = complete blood count; CRP = C-reactive protein; DEP = dose-escalating period; DBP = diastolic blood pressure; FSH = follicle-stimulating hormone; IMP = investigational medicinal product; iTD = individually titrated dose; Phe = phenylalanine; PPI = proton pump inhibitor; RWP = randomized withdrawal period; SBP = systolic blood pressure; Term = termination; Tyr = tyrosine; WOCBP = women of childbearing potential.

a Weeks are relative to the study period (i.e., each part begins with Week 1). All assessments/visits may be conducted within a 3-day window.

b All visits/assessments may be performed in the clinic or by a home healthcare professional at an alternate location (e.g., home, office, etc.), except for screening and end of DEP which must either be in person or via a virtual platform capable of completing all scheduled events including examination.

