## 8.10. Safety Analysis

Safety will be evaluated by scheduled monitoring of AEs, vital signs, and clinical laboratory measurements. Safety parameters will be summarized descriptively by the treatment regimen (dose and frequency) that the participant was on at the time of the safety measurement.

By-participant listings of all measurements and parameters will be presented in tabular format, including absolute values and changes from baseline (if applicable), by dose cohort and study day.

Adverse events will be coded using the *Medical Dictionary for Regulatory Activities*, and severity of AEs and laboratory abnormalities will be graded using the National Cancer Institute CTCAE, v5.0, with certain exceptions as listed in [Table 7](#). Adverse events will be tabulated by study period, treatment group, system organ class, and preferred term. Incidence tables of participants with AEs will be presented for all AEs by maximum severity, AESIs, SAEs, AEs assessed as related to IMP, and AEs resulting in discontinuation of study dosing.

For the DEP, safety analyses will be performed on the DEP SAS. For the RWP and OLE study parts, safety analyses will be performed on the corresponding SAS, with results being presented for the responder and nonresponder populations as well as overall population.

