3.6 Participants Disposition and Evaluability

3.6.1 Participant Disposition

The following participant disposition is summarized using the analysis populations defined in [Section 3.5](#).

- The number of participants who entered the Screening Period (i.e., as defined by signing informed consent)
- The number and percent of participants rescreened (using the number screened as the denominator).

The following percentages will use the DEP FAS as the denominator:

- The number of participants enrolled in DEP (i.e., defined as being assigned study drug)
- The number and percent of participants completing/not completing the DEP (i.e., completed the DEP is defined as having completed the End of DEP/RWP Baseline Visit as indicated in the eCRF)
- The number and percent of participants who achieve an iTD
- The number and percent of responders.

The following percentages will use the RWP FAS as the denominator:

- The number of participants randomized into the RWP overall and by responder/nonresponder status
- The number and percent of participants completing/not completing the RWP (i.e., completed the RWP is defined as having a non-missing RWP Week 4 visit) overall and by responder/nonresponder.

The following percentages will use the OLE SAS as the denominator:

- The number of participants enrolled in OLE (i.e., defined as being assigned OLE study drug)
- The number and percent of participants completing the OLE/not completing the OLE (i.e., completing the study as determined by the eCRF question “Did the subject complete the study per protocol?”).

Note: The number and percent of participants who did not complete each of the 3 study parts will be summarized along with the reason:

- LOST TO FOLLOW-UP
- PROTOCOL DEVIATION
- ADVERSE EVENT
- LOW LEVELS OF PHE OR TYR OR PROFOUND ELEVATION IN PHE
- PREGNANCY
- STUDY TERMINATED BY SPONSOR
- PHYSICIAN DECISION
- WITHDRAWAL BY SUBJECT
- NON-COMPLIANCE WITH STUDY DRUG
- DEATH
- OTHER.

The summaries will be overall for Part 1; overall, responder status, and treatment group (i.e., active or placebo) for Part 2; and overall and responder status for Part 3.

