Vital signs (SBP/DBP, pulse, body temperature) (5.5.2)	●	●	
Pregnancy test (WOCBP only) ^b (5.5.3)	●	●	
Record concomitant medications (4.3.4)	●	●	●
Adverse event reporting (5.5.1)	●	●	●
Blood Phe ^c and Tyr (5.4.1)	●		
3-Day dietary intake assessment ^d (3.3)	●	●	
Administer PPI once per day (4.3.4.1)	●		
IMP immediately after meals (TID) (3.2.3)	●		
Laboratory tests (hematology/CBC w/differential, CRP, serum chemistry) (5.5.3)	●	●	
Optional fecal sample for microbiome analysis (5.2)		●	

AE = adverse event; CBC = complete blood count; CRP = C-reactive protein; DEP = dose-escalating period; DBP = diastolic blood pressure; IMP = investigational medicinal product; Phe = phenylalanine; PPI = proton pump inhibitor; RWP = randomized withdrawal period; SBP = systolic blood pressure; Term = termination; TID = 3 times per day; Tyr = tyrosine; WOCBP = women of childbearing potential.

a All visits/assessments may be performed in the clinic or by a home healthcare professional at an alternate location (e.g., home, office).

b Urine pregnancy test at quarterly visits.

c All blood Phe should be drawn in duplicate.

d A 3-day dietary intake assessment will occur immediately before all scheduled study visits.

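### The SAP pools laboratory results over dose in all three study parts, although the protocol says safety parameters are summarised by dose at the time of measurement, and the change is not declared

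*SAP*

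**What the plan says.** Protocol section 8.10 opens: "Safety will be evaluated by scheduled monitoring of AEs, vital signs, and clinical laboratory measurements". Its next sentence sets the grouping: "Safety parameters will be summarized descriptively by the treatment regimen (dose and frequency) that the participant was on at the time of the safety measurement". A separate output, listings for each participant, is described after that.

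SAP section 3.15.2 plans three laboratory outputs: descriptive statistics of values and changes at each scheduled visit, a low/normal/high classification, and shift tables. The shift tables use the DEP baseline as reference and each participant's lowest and highest post-baseline value in each study period. The grouping is: "For the RWP the results will be presented by treatment group; and presented overall for the DEP and OLE". SAP section 3.15 adds a responder/nonresponder breakdown for the RWP and OLE, but no breakdown by dose. SAP section 3.6.1 shows what treatment group means in the RWP: "overall, responder status, and treatment group (i.e., active or placebo) for Part 2". SAP section 3.15.3, on vital signs, gives no grouping at all.

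The protocol describes the CRP finding twice. Section 1.5.2, on a SYNB1618 study, says: "A small, dose-related increase in C-reactive protein (CRP) was observed in some participants". Section 1.7, summarising SYNB1934 and SYNB1618 together, says: "A small dose-related and reversible increase in CRP has been observed in some participants". Both sections call its clinical significance unclear.

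**The concern.** Dose varies between participants throughout this trial, and within participants in the DEP and OLE. A laboratory table pooled over the three dose levels shows whether values moved, but not at which dose. The protocol promised the second kind of summary and describes one laboratory parameter, CRP, as having risen in a dose-related way. Following SAP 3.15.2 literally, the study report would contain no summary table answering the question that this history raises. A reader of SAP 3.20 would not learn that a protocol commitment had been dropped.

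**Working it through.** The documents state no figure to reproduce here. The check is a comparison of text.

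1. **Does protocol 8.10 cover laboratory data?** Yes. It names clinical laboratory measurements as part of safety and then sets one grouping for safety parameters generally.
2. **Does *overall* in SAP 3.15.2 mean pooled over dose?** Yes, by the SAP's own usage. SAP 3.15.1.5 asks for DEP adverse events both by dose group and overall, as two presentations. SAP 3.15.2 asks for the second only.
3. **Does the RWP split recover dose?** No. Treatment group is active or placebo (SAP 3.6.1). Where the SAP wants individual doses within the active arm, as for adverse events in 3.15.1.5, it says so.
4. **Count by study part:**

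| Part | Protocol 8.10 | SAP 3.15.2 | Laboratory summary by dose? |
|---|---|---|---|
| DEP | dose and frequency at measurement | pooled | no |
| RWP | dose and frequency at measurement | active / placebo | no |
| OLE | dose and frequency at measurement | pooled | no |

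   The result is 0 of 3 parts. Three dose levels fall into one column in the DEP and OLE and into one active column in the RWP.
5. **Is the departure declared?** SAP 3.20 lists nine changes. They concern de-escalation after randomisation, estimands, analysis sets, model covariates and testing order. None concerns the grouping of safety data.
6. **Is CRP affected?** Yes. It is in the serum chemistry panel (SAP Appendix 2). Under the schedules of events it is drawn at screening, DEP baseline, End of DEP, RWP Week 4, OLE quarterly visits and End of Study.
7. **What could a by-dose table show?** Each participant has one scheduled post-baseline DEP draw, at End of DEP, while on the iTD. A DEP table by dose is therefore a comparison between participants grouped by iTD. The quarterly OLE draws can be tabulated by the dose at each draw.

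**Illustration of what pooling does (assumed inputs).** Let *p* be the share of participants at the top dose, and suppose only they rise, by a mean *D*. The pooled mean rise is *p* × *D*. At *p* = 0.20 it is 0.20*D*, and it approaches *D* only as *p* approaches 1. If 20% at the top dose and 5% at lower doses shifted to high, the pooled shift rate at *p* = 0.20 would be 0.20 × 20% + 0.80 × 5% = 4% + 4% = 8%. The 20% share is the limit below which the interim criteria in protocol Table 12 drop the top dose. It is not a forecast, and the shift rates are invented for the example.

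**The case against.** The strongest reply is that nothing is lost, because dose is known for every scheduled value. Protocol 8.10 and SAP 3.15 both plan by-participant listings by dose cohort. SAP 2.4.3 requires the diagnosis behind a clinically significant abnormality to be recorded as an adverse event, and adverse events are tabulated by dose in the DEP (SAP 3.15.1.5) and across periods (SAP 3.15.1.7). The pooled tables also report maxima and shifts based on the highest value, so a rise would be detected even if not attributed to a dose.

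Much of this stands. A reader might infer that the trial cannot show CRP by dose. The documents do not support that: the data will exist and the listings will carry dose. What they do not provide is the summary. Protocol 8.10 asks for summaries as well as listings, so a listing does not discharge the commitment. The adverse-event route is also weak for this parameter, since protocol 1.5.2 reports that no adverse events appeared related to the CRP increases in that study.

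Four further inferences should be resisted.
- **CRP is not the only laboratory risk the protocol names.** Low Phe, low Tyr and marked Phe elevation are discontinuation triggers (protocol 3.5 and 8.11).
- **The dose-dropping decision does not turn on CRP.** The Table 12 criteria concern iTD attainment, Phe reduction and response. What the DMC will see is left to a separate DMC SAP.
- **SAP 3.15.3 does not contradict the protocol.** It is silent on grouping.
- **The absence of a safety laboratory draw in the iTD-finding period is not an error.** No passage promises CRP at each DEP dose level.

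**Conclusion.** The point holds as an undeclared inconsistency between protocol 8.10 and SAP 3.15.2. By-dose laboratory summaries are specified in 0 of 3 study parts, where the protocol's wording calls for them in all three. The practical loss is attribution of laboratory changes to dose, chiefly for CRP; detection of such changes is largely preserved. Efficacy analyses are unaffected. It should be corrected, because the protocol already commits to the summary and the SAP already assigns dose at event date for adverse events.

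The conclusion rests on reading *overall* as the SAP uses it elsewhere. It also assumes that the separate table shells (SAP 3.19), which were not available, follow the SAP text. If the shells already split by dose, only the SAP wording needs correcting.

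**What to change.** **In SAP 3.15.2:**
- **DEP:** present summaries and shift tables, including CRP, by dose level at the time of measurement and overall. For the scheduled End of DEP draw, that level is the iTD.
- **OLE:** present results by dose at the time of measurement and overall. Dose can change repeatedly in the OLE, and the shift tables now use one lowest and one highest value per participant for the whole period, so take those extremes within each dose level. The End of Study draw falls at least 30 days after the last dose, so it should be shown separately and not assigned to a dose.
- **RWP:** show the active arm by iTD as well as in total, against placebo.

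**In SAP 3.15.3:** state the same grouping for vital signs.

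**If pooling is intended:** leave 3.15.2 as it is, and list and justify the departure in SAP 3.20.

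**Cost:** SAP and table-shell wording, more tables, and small cells at some doses. The DEP comparison will be between participants by iTD, so it will not isolate the effect of dose within a person.

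Adding CRP to the Week 3 blood draw at each DEP dose level would give a within-participant comparison. That is an optional design change requiring a protocol amendment, and the correction above does not depend on it.

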3.15.3 Vital Signs, Weight and Height

Semi-supine vital signs (systolic blood pressure, diastolic blood pressure, pulse, and body temperature), weight, and height will be collected as specified in the Schedule of Events ([Table 11](#) and [Table 12](#)).

Participants are required to remain in the semi-supine position for at least 5 minutes prior to obtaining vital signs. Body mass index will be calculated based on weight and height as specified in the Schedule of Events.

This data will be summarized using descriptive statistics of actual values and changes from baseline over time at each scheduled assessment timepoint.

3.15.4 ECG

Supine single 12-lead electrocardiograms (ECGs) will be performed at baseline as specified in the Schedule of Events ([Table 11](#) and [Table 12](#)). A listing of the ECG data will be presented.

3.15.5 Physical Examination

A physical examination will be performed at screening only, these results will be presented in a listing.

3.16 Sample Size Justification

Approximately [REDACTED] participants will be enrolled in the DEP to ensure that approximately [REDACTED] are randomized into the RWP. This assumes a dropout rate of [REDACTED] and approximately [REDACTED] of participants are responders. If, during the course of the study, it becomes apparent that the assumptions were not accurate, or a dose level is dropped after the interim analysis, the number of participants enrolled into the DEP may be adjusted. The study has over [REDACTED] in testing that the percent mean change from baseline at the last measurement of the iTD in blood Phe level is different from 0. This assumes a mean percent reduction in blood Phe levels of [REDACTED] a standard deviation of [REDACTED] drop-out rate, and a 2-sided Type I error rate of [REDACTED] mean percent reduction and standard deviation in blood Phe values used in the power calculations are based on results from a similar study in participants with PKU [FDA \(2007\)](#).

A sample size of [REDACTED] in the responder RWP FAS yields approximately [REDACTED] power to detect a difference in the mean change in blood Phe level from baseline to Week 4 between the SYNB1934v1 and placebo treatment groups. This assumes a mean treatment group difference in blood Phe of - [REDACTED] between the SYNB1934v1 and placebo groups, a change from baseline standard deviation of [REDACTED] 1:1 randomization of SYNB1934v1 and placebo, a [REDACTED], and a 2-sided Type I error rate of [REDACTED]. The power was calculated via a t-test. The mean treatment group difference and standard deviation in blood Phe values used in the power calculations are based on results from a similar study in participants with PKU [FDA \(2007\)](#).

3.17 Interim Analysis

Once the first [REDACTED] participants have attained an iTD and completed the DEP or the [REDACTED] has a baseline DEP and has been in the study for [REDACTED], whichever occurs earlier, the DEP data will be evaluated by an independent DMC. The DMC will use the below pre-specified set of criteria based on both safety and efficacy to determine whether the dose regimen is appropriate or whether any doses should be discontinued as well as whether the study should be stopped for futility. Enrollment will not be paused during the interim analysis.

If a dose level is dropped/discontinued, participants who are in the DEP and have an iTD corresponding to a dropped dose will not be randomized into the RWP but will instead enter the OLE directly. In addition, participants who are in the OLE at a dose level that has been dropped will be transitioned to the highest dose level retained.

The size of the DEP interim analysis cohort and corresponding criteria for dropping a dose ([Table 10](#)) provide reasonable operating characteristics for proper determination if one or more doses should be dropped.

Table 10: DMC Criteria for Dose Changes and Futility

Evaluation by DMC	Criteria to Drop the Dose
-------------------	---------------------------

1×10^{12} dose	
$< 20\%$ of the participants who attain an iTD are at the 1×10^{12} dose
 
OR
 
$> 75\%$ of participants who have 1×10^{12} as their iTD had a greater Phe reduction at their 6×10^{11} dose versus their 1×10^{12} dose.

6×10^{11} dose Note: considered only if the Drop 1×10^{12} Criteria has been met	
$< 30\%$ of the participants who attain an iTD have 6×10^{11} or 1×10^{12} as their iTD
 
OR
 
$> 75\%$ of participants who have 6×10^{11} or 1×10^{12} as their iTD had a greater Phe reduction at their 3×10^{11} dose versus their 6×10^{11} dose

Stop for futility	
$< 30\%$ of participants enrolled into the DEP attain an iTD and complete the DEP
 
OR
 
$< 25\%$ of participants who attain an iTD and complete the DEP are responders

Note: these dose-dropping criteria are only applied for the first interim analysis.

DEP = dose-escalating, open-label period; DMC = data monitoring committee; iTD = individually titrated dose; Phe = phenylalanine

In the event that, based on the interim analysis results utilizing the criteria provided in [Table 10](#), the DMC recommends dropping either the 1×10^{12} or the 1×10^{12} and 6×10^{11} doses, the RWP FAS will be modified as described in [Section 3.5](#).

In addition, the DMC will review interim data at defined intervals in the study (i.e., as defined in the DMC charter). The Sponsor will remain blinded to the subject-level blood Phe levels during the DEP and RWP but will have access to the DEP interim analysis results.

The data from the OLE (Part 3) will be reviewed for safety and tolerability on an ongoing basis.

